#### On-treatment schema (Dose Schedule 2):

		Adjuvant Phase																							
Cycle #	1	2	3		4		5		6		7		8		9		10		11						
Week #	1	2	3	4	5	6	7	8	9	10	11	12	13	14	15	16	17	18	19	20	21				
Cisplatin	C	C	C	C	C	C	C																		
Radiation	X	X	X	X	X	X	X																		
Nivolumab	N	N	N	N	N	N					N	N		N	N	N	N	N	N	N	N	N	N		

Nivolumab schedule (Dose Schedule 2): Priming and concurrent nivolumab will be given in conjunction with chemoradiation. Patients will receive 1 cycle of nivolumab on C1D1 (no priming), and start weekly cisplatin 40 mg/m^2, IV, concurrent with 33-35 fractions (6.5-7 weeks) of RT, with concurrent cycles 2-5 of nivolumab every 14 days. No nivolumab will be given on C5D1, to allow for recovery from toxicities. At C6D1, patients will initiate adjuvant nivolumab, every 14 days for cycles 6-11. Immune-related toxicities should be at grade 1 or lower prior to starting a patient on the adjuvant phase of therapy; if not, initiation of the adjuvant phase should be delayed until resolution of toxicities.

#### On-treatment schema (Dose Schedule 3):

Cycle #	Adjuvant Phase																				
	1	2	3	4	5	6	7	8	9	10	11	12	13	14	15	16	17	18	19	20	21
Week #	1	2	3	4	5	6	7	8	9	10	11	12	13	14	15	16	17	18	19	20	21
Cisplatin	C	C	C	C	C	C	C														
Radiation	X	X	X	X	X	X	X														
Nivolumab											N	N	N	N	N	N	N	N	N	N	N

Nivolumab schedule (Dose Schedule 3): Nivolumab will be only given after chemoradiation. On C1D1, patients will start weekly cisplatin 40 mg/m^2, IV, concurrent with 33-35 fractions (6.5-7 weeks) of RT every 14 days. At C6D1, patients will initiate adjuvant nivolumab, every 14 days for cycles 6-11. Immune-related toxicities should be at grade 1 or lower prior to starting a patient on the adjuvant phase of therapy; if not, initiation of the adjuvant phase should be delayed until resolution of toxicities.

### 3.3 Feasibility assessment in the run-in phase

A run-in phase will be conducted initially to determine feasibility. The main schema will be used as illustrated, but dosing of nivolumab will be subject to dose reduction if high grade immune related adverse events are observed.

Six patients will be enrolled for the initial run-in phase, starting with nivolumab dosing of 240 mg. Enrollment will cease until all 6 patients have completed concurrent chemoradiation and nivolumab. If 3/6 patients have experienced grade 3-4 immune related toxicity or other DLT during concurrent chemoradiation and nivolumab therapy, then the dose schedule will be changed to the next dose schedule and the run-in will restart at that schedule. In dose schedule 2, patients will start nivolumab concurrently with chemoradiation and there will be no priming dose prior to chemoradiation. Using these same procedures, there may be one further change to dose schedule 3. In dose schedule 3, patients will not have priming or concurrent nivolumab and will only start nivolumab in the adjuvant phase after chemoradiation is concluded. No dose reductions of nivolumab will be allowed. No dose escalation will be allowed.

The run-in will cease when 4/6 patients or more have completed their specified concurrent nivolumab therapy at the same nivolumab dose schedule without experiencing grade 3-4 toxicity or other DLT, or alternatively, if 3/6 patients have experienced grade 3-4 toxicity or other DLT during the adjuvant phase at dose schedule 3 (in which case the entire study will terminate). Therefore, a minimum of 6 patients and a maximum of 18 patients will be enrolled in the run-in phase.

DLT criteria are grade  $\geq 3$  immune-related adverse events, need to hold nivolumab for  $>28$  days due to toxicity, and for patients receiving concurrent nivolumab with chemoradiation, inability to complete chemoradiation or need to hold chemoradiation for  $>3$  days due to immune-related toxicity.

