### **1.2.2.2 Safety studies in humans**

Single-dose PK of nivolumab was studied in 39 subjects with cancer. The single-dose PK of nivolumab was linear and dose-proportional in the range of 0.3 mg/kg to 10 mg/kg.

The mean terminal T-1/2 of nivolumab ranged between 17 and 25 days across the dose range of 0.3 mg/kg to 10 mg/kg. Geometric mean total clearance varied from 0.13 mL/h/kg to 0.19 mL/h/kg, while mean volume of distribution varied between 83 mL/kg and 113 mL/kg across doses. The clearance and half-life of nivolumab are consistent with that of IgG4.

The pharmacokinetics (PK) of nivolumab was studied in subjects over a dose range of 0.1 to 10 mg/kg administered as a single dose or as multiple doses of nivolumab every 2 or 3 weeks. Based on a population pharmacokinetic (PPK) analysis using data from subjects with various tumor types, including melanoma and NSCLC, the geometric mean (% CV%) clearance (CL) is 9.5 mL/h (49.7%), geometric mean volume of distribution at steady state (Vss) is 8.0 L (30.4%), and geometric mean elimination half-life (t1/2) is 26.7 days (101%). Steady-state concentrations of nivolumab were reached by 12 weeks when administered at 3 mg/kg every 2 weeks, and systemic accumulation was approximately 3-fold. The exposure to nivolumab increased dose proportionally over the dose range of 0.1 to 10 mg/kg administered every 2 weeks. The clearance of nivolumab increased with increasing body weight. The PPK analysis suggested that the following factors had no clinically important effect on the clearance of nivolumab: age (23 to 87 years), gender, race, baseline LDH, PD-L1, tumour type, baseline tumor size, and hepatic impairment. Although ECOG status, baseline glomerular filtration rate (GFR), albumin, and body weight had an effect on nivolumab CL, the effect was not clinically meaningful.

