## 3 Study Design

### 3.1 Characteristics

This is a Phase 2, single arm, open-label, multicenter study evaluating the feasibility of a treatment regimen comprised of nivolumab administered approximately every 2 weeks before and during chemoradiation and as an adjuvant therapy for 3 months to patients with stage II-IVB NPC who are planning to undergo chemoradiation treatment of their cancer.

A run-in phase will precede expansion, to establish basic feasibility of the nivolumab schedule. The run-in cohorts will include 6 patients at each dose schedule, with 2 planned changes in dose schedule if >33% toxicity or other DLT is observed. A minimum of 6 patients and maximum of 18 patients may be enrolled in the three run-in cohorts. The MTD schedule will be selected when 4/6 patients at a dose schedule complete therapy without grade 3-4 immune related toxicity. All patients will receive the same dose of nivolumab (240mg).

At the starting dose schedule, patients will receive nivolumab for 1 cycle prior to initiation of chemoradiation (approximately 14 days). Patients will subsequently continue with nivolumab every 14 days until completion of chemoradiation. In dose schedule 2, patients will start nivolumab concurrent with start of chemoradiation. In dose schedule 3, patients will start nivolumab after completion of chemoradiation (adjuvant nivolumab only).

DLT criteria are grade  $\geq 3$  immune-related adverse events, need to hold nivolumab for >28 days due to toxicity, and for patients receiving concurrent nivolumab with chemoradiation, inability to complete chemoradiation or need to hold chemoradiation for >3 days due to immune-related

toxicity.

The expansion phase will continue after the run-in phase has been used to establish the MTD schedule for nivolumab. The expansion phase will be powered to test the feasibility of completion of the program as compared to the current standard of care.

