## 5.2 Dose Modifications and Dosing Delays

### 5.2.1 Dose Delays of Nivolumab

No dose escalation or dose reduction of nivolumab from the patient's starting dose is allowed. Dose delays are allowed for an individual patient at the investigator's discretion to allow for resolution of toxicities as described below.

A general principle is that differential diagnoses should be diligently evaluated according to standard medical practice. Non-inflammatory etiologies should be considered and appropriately treated.

Corticosteroids are a primary therapy for immuno-oncology drug-related adverse events. The oral equivalent of the recommended IV doses may be considered for ambulatory patients with low-grade toxicity. The lower bioavailability of oral corticosteroids should be taken into account when switching to the equivalent dose of oral corticosteroids.

Consultation with a medical or surgical specialist, especially prior to an invasive diagnostic or therapeutic procedure, is recommended.

Specific management algorithms for immune-related toxicities are given in Appendix

5 and should be referenced in case of any immune-related AE.

If dosing with study drug is delayed for > 28 consecutive days due to toxicity, protocol therapy should be discontinued unless otherwise agreed between the investigators and Principal Investigator.

For patients expected to require more than 4 weeks of corticosteroids or other immunosuppressants to manage an adverse event, consider the following recommendations:

- Antimicrobial/antifungal prophylaxis per institutional guidelines to prevent opportunistic

infections such as *Pneumocystis jiroveci* and fungal infections.

- Early consultation with an infectious disease specialist should be considered. Depending on the presentation, consultation with a pulmonologist for bronchoscopy or a gastroenterologist for endoscopy may also be appropriate.
- In patients who develop recurrent adverse events in the setting of ongoing or prior immunosuppressant use, an opportunistic infection should be considered in the differential diagnosis.

Treatment or visit delays for public holidays or weather conditions do not constitute a protocol violation.

The following dose delay rules will be used with respect to potential toxicity. Toxicity will be assessed according to the NCI Common Terminology Criteria for Adverse Events Version 4.0 (CTCAE v5.0).

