a Each 14-day period of treatment will represent 1 cycle and begins from C1D1.b Baseline conditions assessmentc As part of efficacy assessments, quality of life by FACT-NP, FACT-Taxane, HHIE-S, and EuroQOL EQ-5D will be administered at baseline, at cycle 6, at end of treatment and at all followup visits. Survey's not available in the patient's language may be administered by the study staff in an interview format with a translator, however failure to obtain any individual quality of life survey not available in the patient's language will not be considered a protocol deviation.d Toxicity will be assessed by CTCAE v5.0f There is a 72 hour window of scheduled nivolumab administration. **In Dose Schedule 1:** Nivolumab will be administered on C1D1 for priming and then q14 days beginning C2D1, concurrent with chemoradiation, until C5D1. Nivolumab will not be administered on C6D1 to allow for any resolution of toxicities. Beginning C7D1, adjuvant nivolumab q14 days will be administered until C12D1. **In Dose Schedule 2:** Nivolumab will be administered on C1D1 concurrent with chemoradiation (no priming), and then q14 days until C4D1. Nivolumab will not be administered on C5D1 to allow for any resolution of toxicities. Beginning C6D1, adjuvant nivolumab q14 days will be administered until C11D1. **In Dose Schedule 3:** Nivolumab will not be administered until after completion of chemoradiation. Beginning C6D1, adjuvant nivolumab q14 days will be administered until C11D1. Immune-related toxicities should be at grade 1 or lower prior to starting a patient on the adjuvant phase of therapy; if not, initiation of the adjuvant phase should be delayed until resolution of toxicities.h Physical Exam includes weight measurementsi Disease-specific criteria (for CRF purposes, e.g.: GU assessment, BR disease Eval, AML-MDS Summary, etc.)j Measurable disease will be assessed using RECIST 1.1 criteriak For the **baseline** tissue collection, if a biopsy was performed within 90 days prior to C1D1, and no intervening treatment was given, a repeat biopsy is not required if adequate tumor tissue can be provided. **Repeat biopsy** will be at the discretion of the investigator, and timing will depend on Dose Schedule. **In Dose Schedule 1:** Tumor tissue post-nivolumab during cycle 1 AND after first week of radiation therapy. **In Dose Schedule 2 and 3:** Tumor tissue after first week of radiation therapy only. See appendix 4 for further details.l All blood draws may be completed within 7 days prior to start of therapy unless otherwise specified; screening labs must be completed within 14 days of Cycle 1 Day 1.m Hemoglobin, hematocrit, platelets, total white blood cell count (WBC) and differentialn Alkaline phosphatase, aspartate aminotransferase/alanine aminotransferase (ALT/AST), total bilirubin, total protein, albumin, calcium, phosphorus, magnesium, blood urea nitrogen (BUN), creatinine, glucose fasting), potassium, sodium, chloride, bicarbonate, uric acid, LDH, fasting lipid panel (LDL, total cholesterol, triglycerides), thyroid stimulating hormone (TSH).o **Pre-menopausal females:** serum or urine pregnancy test within 7 days prior to start of study drug. Serum pregnancy test by local laboratory  $\leq$  1 day prior to C1D1 for women of childbearing potential. If the serum pregnancy test results are not available on C1D1, a urine pregnancy test can be performed on C1D1 to confirm that the patient is not pregnant prior to dosing.p See Appendix 4 for details on tissue specimen collection and processing.q Collection of peripheral blood for correlative biomarkers and peripheral immune changes must be collected with every cycle of nivolumab. Blood will also be collected in post-treatment followup to 1 year.r Imaging with MRI nasopharynx/face/neck and whole body PET-CT will be performed at screening and at end of treatment and at 1 year followup, with further imaging to be performed as clinically indicated.

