### 8.2.2 Run-in phase

Six patients will be enrolled for the initial run-in phase, with nivolumab dosing of 240 mg. Enrollment will cease until all 6 patients have completed concurrent chemoradiation and nivolumab. If 3 or more of the first 6 patients experience grade 3-4 immune related toxicity or other DLT during concurrent chemoradiation and nivolumab therapy, then the run-in will restart at dose schedule 2 with 6 additional patients. In dose schedule 2, patients will start nivolumab

concurrent with chemoradiation and will not start nivolumab prior to chemoradiation. If 3 or more of the first 6 patients experience grade 3-4 immune related toxicity or other DLT during concurrent chemoradiation and nivolumab at dose schedule 2, then the dose schedule will be changed to dose schedule 3 and the run-in will restart at dose schedule 3 with 6 additional patients. In dose schedule 3, patients will start nivolumab in the adjuvant phase only and will not receive nivolumab before or during chemoradiation, and the toxicity of nivolumab will be assessed during the adjuvant phase. No dose escalation or reduction will be allowed in the run-in phase. Dose modifications of nivolumab are not permitted from the standard dose of 240 mg every 14 days.

The run-in will cease when 4 or more patients have completed chemoradiation and nivolumab therapy at the same nivolumab dose schedule without experiencing grade 3-4 toxicity or other DLT (this will be considered the maximally tolerated dose), or alternatively, if 3/6 patients have experienced grade 3-4 toxicity at dose schedule 3 during administration of adjuvant nivolumab (in which case the entire study will terminate). Therefore, a minimum of 6 patients and a maximum of 18 patients will be enrolled in the run-in phase.

DLT criteria are grade  $\geq 3$  immune-related adverse events, need to hold nivolumab for  $>28$  days due to toxicity, and for patients receiving concurrent nivolumab with chemoradiation, inability to complete chemoradiation or need to hold chemoradiation for  $>3$  days due to immune-related toxicity.

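### For Schedules 1 and 2 the run-in counts DLTs only until concurrent therapy ends, too early for a hold of more than 28 days from either of the last two concurrent doses to register

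*Combined protocol and SAP*

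**What the plan says.** Section 3.3 gives the trigger for moving to the next schedule: "If 3/6 patients have experienced grade 3-4 immune related toxicity or other DLT during concurrent chemoradiation and nivolumab therapy". Section 8.2.2 limits the count to the same phase. Both sections use the same pause: "Enrollment will cease until all 6 patients have completed concurrent chemoradiation and nivolumab". The pass rule in Section 3.3 refers to the same phase: "The run-in will cease when 4/6 patients or more have completed their specified concurrent nivolumab therapy".

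One of the listed DLTs is a duration: "need to hold nivolumab for >28 days due to toxicity". Section 5.2.1 describes such a hold as delayed dosing: "If dosing with study drug is delayed for > 28 consecutive days due to toxicity, protocol therapy should be discontinued".

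Not every passage draws the window the same way. Section 3.1 selects the MTD schedule when four of six patients complete therapy, without limiting this to the concurrent part. The stopping sentence of Section 8.2.2 speaks of completing chemoradiation and nivolumab therapy. Either could be read as a longer window. Appendix 2 (run-in monitoring plan) mentions a DLT period, but no passage defines one in days. For Schedule 3, Section 8.2.2 places the toxicity assessment in the adjuvant phase.

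**The concern.** A DLT defined by duration can be observed only if the window outlasts that duration. Here the window closes with radiation, a few days after the last concurrent dose. A run-in patient could be on a toxicity hold when the cohort is judged, be counted as free of DLT, and meet the protocol's own definition some days later. An immune-related event of grade 3 or higher that appears after radiation ends is also left out of the count.

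Both omissions act in one direction: they make it easier for the more intensive schedule to pass. The run-in is the only place where Schedules 1 and 2 face a numerical toxicity rule. Its result fixes the schedule for the expansion phase, and by Section 3.4 the run-in patients treated at the selected schedule enter the primary analysis.

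**Working it through.** **Inputs.** Cycle length, from Table 6.1: "Each 14-day period of treatment will represent 1 cycle and begins from C1D1". Schedule 1 doses, same table: "Nivolumab will be administered on C1D1 for priming and then q14 days beginning C2D1, concurrent with chemoradiation, until C5D1". For Schedule 2 the Table 6.1 footnote has concurrent doses from C1D1 to C4D1. Radiation is 33-35 fractions (Section 3.2) at five per week (Section 5.1.1.1, Dose Specifications).

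**Plan's own figures first.** Thirty-three fractions from a Monday are six full weeks (30 fractions) plus three days, so the last falls on radiation day 45. That is 6 weeks 3 days, as the Dose Specifications state. With CkD1 = 1 + 14(k - 1), the last adjuvant dose in Schedule 1 (C12D1) is day 155, in week 23, which matches the 23 weeks of total therapy in the Abstract. The calendar is reproduced.

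**Schedule 1.** Radiation starts at C2D1, day 15. It ends on day 59 (33 fractions) or 61 (35 fractions). Hold length at the end of radiation = last radiation day minus the scheduled day of the first withheld dose.

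| Hold starts at | Day | Length when radiation ends | First exceeds 28 days |
|---|---|---|---|
| C2D1 | 15 | 44-46 days | day 44 |
| C3D1 | 29 | 30-32 days | day 58 |
| C4D1 | 43 | 16-18 days | day 72 |
| C5D1 | 57 | 2-4 days | day 86 |

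**Schedule 2.** Radiation runs from day 1 to day 45-47. Holds from C2D1, C3D1 and C4D1 (days 15, 29, 43) reach 30-32, 16-18 and 2-4 days. The last two doses are again out of reach.

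**How firm this is.** With any weekday start, the last two intervals become 2-6 and 16-20 days. Adding the 72-hour dosing window, a hold from the second-last dose reaches at most 20 + 3 = 23 days. To reach day 29 of a hold, radiation would have to be prolonged by 29 - 18 = 11 to 29 - 16 = 13 days (second-last dose), or by 29 - 4 = 25 to 29 - 2 = 27 days (last dose).

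**Effect on the decision.** The documents do not say what share of DLTs emerges after the concurrent phase, so this part is an assumption. With true rate p and late share s, the counted rate is p(1 - s). A cohort passes with two or fewer DLTs among six patients: P(X ≤ 2), X ~ Binomial(6, p(1 - s)).

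| True rate | None late | 20% late | One third late | 40% late |
|---|---|---|---|---|
| 20% | 0.901 | 0.944 | 0.965 | 0.974 |
| 33% | 0.687 | 0.808 | 0.875 | 0.904 |
| 50% | 0.344 | 0.544 | 0.680 | 0.744 |

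**Would the first adjuvant visit be late enough?** In Schedule 1 that visit (C7D1) is day 85. A hold from C4D1 is then 42 days old, and one from C5D1 exactly 28 days, which is not yet more than 28. The same holds at C6D1 (day 71) in Schedule 2. A window ending on that visit would still miss a hold from the last dose unless open holds are followed further.

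**The case against.** Several points on the other side stand.

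- **Decision date.** No passage states one. The 2-4 days is the earliest point, set by the last patient to finish. Earlier finishers have been followed longer by then, although the wording still closes their count at the end of the concurrent phase.
- **What the hold criterion adds.** Any immune-related event of grade 3 or higher is a DLT at onset, so the hold criterion mainly adds long holds for lower grades.
- **How a hold is counted.** Counted from the last dose given, a hold at the second-last dose would be 30-32 days old when radiation ends. Section 5.2.1's reference to delayed dosing favours the withheld dose. The alternative also sits badly with the planned gap from C5D1 to C7D1, itself 28 days. On either count a hold at the last dose stays out of reach. One could also declare the need for a long hold before day 28, but no passage provides for this.
- **Other safeguards.** Section 8.3 keeps continuous review by the PI and the DSMC. Appendix 2 requires notice when grade 3-4 rates exceed brochure rates. Discontinuation for toxicity fails the primary endpoint, and the Simon first stage can stop the trial (11 or fewer completions of 22 in Section 8.2.1). These are indirect and do not replace the 3-of-6 rule.

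A reader might also infer that the protocol's pharmacokinetics prove the window too short, since "Steady-state concentrations of nivolumab were reached by 12 weeks when administered at 3 mg/kg every 2 weeks" while the decision can come at about 8.5 weeks. The documents do not support that step: the figure is for weight-based dosing, and no passage links steady state to the timing of immune-related events.

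**Conclusion.** The gap is real and specific. On the nominal calendar, with holds counted from the first withheld scheduled dose, two of the four concurrent doses in each of Schedules 1 and 2 cannot give rise to a hold DLT inside the window. Immune-related events of grade 3 or higher that emerge after concurrent therapy are outside the numerical rule.

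Three stronger readings should be resisted. Toxicity after the last two doses is not ignored altogether: events of grade 3 or higher in the remaining 2-4 or 16-18 days count. The hold DLT is not strictly impossible, since a long enough radiation break would bring it into the window. Schedule 3 does not share the problem.

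The size of the bias is unknown. Under the one-third assumption, and with patients treated as independent, the chance of passing at a true rate of 50% doubles from 0.34 to 0.68. At 20% it moves only from 0.90 to 0.965. The direction does not depend on the assumption.

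The documents are also inconsistent. Section 3.1 and the stopping sentence of Section 8.2.2 can be read as a longer window than Section 3.3. On Schedule 2, the text of Section 3.2 names concurrent cycles 2-5 and yet no dose on C5D1, while Table 6.1 ends concurrent dosing at C4D1. The working uses Table 6.1 only as a basis for calculation. These passages must be reconciled.

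**What to change.** State one DLT observation window for Schedules 1 and 2, in the same words, in Sections 3.1, 3.3 and 8.2.2, long enough for every listed DLT criterion to be observed. One way is to count from the first nivolumab dose through the planned first adjuvant visit (C7D1 in Schedule 1, C6D1 in Schedule 2). Any toxicity hold still open at that visit is then followed until it resolves or exceeds 28 days. Take the go decision and resume accrual only when all six patients have completed this window.

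Count only time held because of toxicity, not the planned no-dose cycle. Otherwise a Schedule 1 hold covering C4D1 and C5D1 would run to C7D1, 42 days, even if the toxicity had resolved earlier. Reconcile the Schedule 2 dose list between Section 3.2 and Table 6.1 in the same amendment.

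The cost is a longer accrual pause: 85 - 61 = 24 to 85 - 59 = 26 days, about 3.5 weeks per run-in cohort, and somewhat more if a hold is still open. No visits or tests are added, because the visit exists and Section 3.2 already requires immune-related toxicity to be assessed before adjuvant treatment starts.

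### The run-in change, go and termination rules count different toxicities, so some six-patient outcomes lead to no decision or to opposite ones

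*Combined protocol and SAP*

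**What the plan says.** The run-in enrols six patients per schedule, with up to three schedules. Its decision rules appear in four places.

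- **Change rule.** Section 3.3: "If 3/6 patients have experienced grade 3-4 immune related toxicity or other DLT during concurrent chemoradiation and nivolumab therapy", move to the next schedule. Section 8.2.2 agrees: "If 3 or more of the first 6 patients experience grade 3-4 immune related toxicity or other DLT". Both limit the grade 3-4 count to immune-related events. The change wording in the abstract and 3.1 uses a threshold above 33% for toxicity or other DLT and has no such limit.
- **Go rule.** In 3.3 the run-in ends when at least four of six patients "have completed their specified concurrent nivolumab therapy at the same nivolumab dose schedule without experiencing grade 3-4 toxicity or other DLT". Section 8.2.2 likewise asks for four or more patients "without experiencing grade 3-4 toxicity or other DLT (this will be considered the maximally tolerated dose". Neither says immune-related.
- **Selection sentence.** Section 3.1 selects the schedule when four of six patients complete therapy free of immune-related grade 3-4 toxicity. It does not mention other DLTs.
- **Termination at Schedule 3.** Section 3.3 ends the study "if 3/6 patients have experienced grade 3-4 toxicity or other DLT during the adjuvant phase at dose schedule 3". Section 8.2.2 ends it "if 3/6 patients have experienced grade 3-4 toxicity at dose schedule 3 during administration of adjuvant nivolumab". Neither says immune-related, and 8.2.2 also omits other DLTs.

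The DLT definition that follows the rules in 3.3 and 8.2.2 restricts its grade-based criterion (grade 3 or higher) to immune-related events. For Schedule 3, 8.2.2 adds that "the toxicity of nivolumab will be assessed during the adjuvant phase". That fixes a period but not a type of toxicity.

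**The concern.** The change rule and the go rule should be complements, so that each cohort of six leads to exactly one decision. They are complements only if both count the same event. As written, the change rule in 3.3 and 8.2.2 counts immune-related grade 3-4 toxicity or other DLT, while the go and termination rules count grade 3-4 toxicity of any cause or other DLT. A cohort with common non-immune grade 3 events can fall between them.

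These rules decide which schedule is expanded, which run-in patients enter the primary analysis (3.4 and 8.2.3) and whether the study terminates. The gap at Schedules 1-2 can arise at the first run-in decision. The conflict at Schedule 3 requires two failed cohorts first, but the decision there is whether to end the trial.

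There is also a smaller mismatch. The go rule in 3.3 asks for completed concurrent nivolumab, yet the same section says "In dose schedule 3, patients will not have priming or concurrent nivolumab".

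**Working it through.** **Step 1. The plan's own figure.** Sections 3.3 and 8.2.2 derive a run-in size of 6 to 18 from the rules. Let k be the number of patients with the counted event, the same event in every rule. Change is k ≥ 3. Go is 6 − k ≥ 4, that is k ≤ 2. For k = 0 to 6 exactly one of these holds, so every cohort ends in a decision. The range is then 6 to 3 × 6 = 18, and the plan's figure is reproduced under a single event definition.

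**Step 2. The rules as literally worded.** Let i be the number of patients with immune-related grade 3-4 toxicity and n the number with any grade 3-4 toxicity, 0 ≤ i ≤ n ≤ 6. Assume that all six complete therapy and no other DLT occurs. Counts of three or four of six are read as at least that many.

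| Rule | Condition |
|---|---|
| Change (3.3, 8.2.2) | i ≥ 3 |
| Go (3.3, 8.2.2) | 6 − n ≥ 4, so n ≤ 2 |
| Select (3.1) | 6 − i ≥ 4, so i ≤ 2 |
| Terminate at Schedule 3 (3.3, 8.2.2) | n ≥ 3 |

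The affected outcomes are i ≤ 2 with n ≥ 3, which is 3 × 4 = 12 of the 28 possible pairs. This is a count of outcomes, not a likelihood. Example: i = 0, n = 3.

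- Schedules 1-2, 3.3/8.2.2: change is not met (0 < 3) and go is not met (3 < 4).
- Schedules 1-2, 3.1: n/6 = 0.5 meets the unqualified change wording, and 6 − i = 6 meets the selection sentence, so both apply.
- Schedule 3, events in the adjuvant phase: 3.1 selects, while 3.3 and 8.2.2 terminate.

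Within 3.3 or 8.2.2 alone, go and terminate never hold together. The opposition is between sections.

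**Step 3. Chance of the gap in the Schedule 1 cohort.** Since i ≥ 3 implies n ≥ 3, the chance is P(n ≥ 3) − P(i ≥ 3). The documents give no rates for this regimen, so rates are assumed and patients treated as independent. For X ~ Binomial(6, p):

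| p | 0.05 | 0.10 | 0.20 | 0.30 | 0.50 | 0.70 |
|---|---|---|---|---|---|---|
| P(X ≥ 3) | 0.0022 | 0.0159 | 0.0989 | 0.2557 | 0.6563 | 0.9295 |

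Differences:

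| Any-cause rate | Immune-related 5% | 10% | 20% |
|---|---|---|---|
| 30% | 0.254 | 0.240 | 0.157 |
| 50% | 0.654 | 0.640 | 0.557 |
| 70% | 0.927 | 0.914 | 0.831 |

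Section 5.2.2 describes grade 3 mucositis as common in head and neck cancer patients, so low any-cause rates are less relevant during chemoradiation.

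**Step 4. Conflict at Schedule 3.** If Schedule 3 is reached, the chance of select against terminate at any-cause/immune-related rates of 10%/5%, 20%/10% and 30%/10% is 0.014, 0.083 and 0.240. The chance of literal termination, including outcomes where the sections agree, is 0.016, 0.099 and 0.256 at any-cause rates of 10%, 20% and 30%. Reaching Schedule 3 needs two failed cohorts, with probability P(X ≥ 3)²: 0.00025, 0.0098 and 0.0654 at a per-patient DLT rate of 10%, 20% and 30% in both. The largest unconditional value listed is 0.0654 × 0.2398 = 0.0157.

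**Step 5. Allowing other DLTs.** Put each patient in one of four classes: immune-related grade 3-4; other DLT without grade 3-4 toxicity; non-immune grade 3-4 only; none. There are 84 outcomes. At Schedules 1-2, 24 meet neither rule of 3.3/8.2.2. At Schedule 3, 24 terminate under 3.3 but not under 8.2.2, because 8.2.2 omits other DLTs. One is three patients with a nivolumab hold beyond 28 days and no grade 3-4 event: 8.2.2 then gives neither go (3 < 4) nor termination.

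**The case against.** The strongest reply is that the text implies one immune-related count throughout. The word *other* before DLT makes the grade 3-4 item a kind of DLT, and the only grade-based DLT is immune-related. The opening of 3.3 speaks of high-grade immune-related events. The stated range of 6 to 18 follows only if one event is counted in every rule (Step 1). Section 5.2.1 does not delay nivolumab for grade 3 radiation dermatitis, radiation-related grade 2-3 mucositis or isolated grade 3-4 lymphopenia, so a go rule counting such events would sit oddly with the rest of the plan. In Appendix 2, run-in cohort updates are described in terms of DLTs. On this view the probabilities above attach to a reading that nobody intended, and DSMC review would catch a misapplication.

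Most of this stands as evidence of intent, and the immune-related reading is the more natural one. It does not supply the missing rule. No sentence states which count applies to go or termination. The termination clause in 8.2.2 lacks the phrase about other DLTs on which the inference rests. The run-in report to the DSMC lists both all adverse events and DLTs, so it does not settle the count.

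On evaluation periods the reply is largely right: both sections place Schedule 3 toxicity in the adjuvant phase, and the go rule in 8.2.2 does not say concurrent. What remains is that word in the 3.3 go rule.

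**Conclusion.** The concern holds. The operative run-in rules are inconsistent as written and should be fixed. Under 3.3/8.2.2 a Schedule 1 or 2 cohort can meet neither rule. Across sections, a Schedule 3 cohort can be both selected and the reason to terminate the study.

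The first-decision gap is the larger practical problem: 0.157 to 0.927 over the rates in Step 3. The Schedule 3 conflict is at most about 0.016 unconditionally over the listed assumptions. All these figures rest on a literal reading, assumed rates, six completing patients and no other DLT. They are not forecasts that the run-in will stall, since the committee may well apply the more natural reading. The defect is that it would be inferring a rule that the protocol does not state.

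**What to change.** Reconcile the abstract, 3.1, 3.3 and 8.2.2 so that the change, go and termination rules use:

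- one toxicity definition, with other DLTs treated the same way in every clause;
- one integer count out of six instead of a percentage in some places (2/6 = 33.3% is above 33% but not above one third);
- an evaluation period that can be applied to each schedule, including Schedule 3, which has no concurrent nivolumab.

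Then check that every outcome of six patients leads to exactly one decision. Which definition, threshold and period apply is for the investigators and the DSMC to decide. The cost is protocol wording only, with no added patients or procedures.
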